[figure not shown]

## **Study protocol**

### *Study design*

This study is a retrospective, single centre study, comparing the rate of improvement in men and women with long COVID-19 syndrome, following the completion of a hybrid PR programme from August 2022 to December 2022. The study flowchart is presented in Figure 1. All patients will have been diagnosed with long COVID-19 based on the persistence of fatigue at least three months following hospital discharge due to COVID-19. Exclusion criteria include participation in another clinical trial, occurrence of myocardial infarction, hospitalisation for unstable angina, stroke, coronary artery bypass graft (CABG), percutaneous coronary intervention (PCI), implantation of a cardiac resynchronization therapy device (CRTD), active treatment for cancer or other malignant disease, uncontrolled congestive heart disease (NYHA class >3), acute psychosis or major psychiatric disorders or continued substance abuse within 3 months prior to informed consent. No change in the medical treatment will be made during the duration of the PR program. During the first phase of the PR programme, patients will undergo a structured, outpatient, supervised hospital-based PR program for 4 weeks with a frequency of 2 training sessions per week. Following the completion of the first phase patients will undergo 24 home-based tele-rehabilitation sessions for 8 weeks with a frequency of 3 training sessions per week. Assessment will be performed at baseline and following completion of the PR programme and include pulmonary function tests, exercise capacity, daily physical activity levels, functional capacity, peripheral and respiratory muscle strength and quality of life. Informed written consent will be obtained from all patients. The investigations will be carried out following the rules of the Declaration of Helsinki of 1975 and the study was approved by the University Hospital Ethics Committee (Protocol ID-24633).

**Figure 1.** Study flow chart

### *Respiratory function assessment*

Standard spirometry will be performed with a metabolic cart using the “fast inspiratory manoeuvre”. Maximum static inspiratory (PImax) and expiratory (PEmax) mouth pressures will be measured with a plastic semi-rigid flanged mouthpiece fitted to a metallic stem incorporating a 3-way tap, manufactured according to the design of Ringqvist. Static lung volumes will be determined by the multiple nitrogen washout technique. The diffusing capacity for carbon monoxide (DLCO) via the single-breath technique will also be determined. Predicted values for spirometry, static lung volumes, and DLCO are from the European Community for Coal and Steel.

### *Peripheral muscle strength, body mass composition and quality of life*

Prior to the onset and following completion of the 3 month hybrid PR program all participants will be assessed for quadriceps isometric muscle strength with a strain gauge Myometer and handgrip strength. Furthermore, body mass composition will be assessed with the method of bio-impedance. Quality of life will be assessed via FACIT, CAT, HADS, SF-36 and the Revised Impact of Events Scale questionnaires.

### *Incremental cycle-ergometer exercise test*

Participants will perform a ramp incremental exercise protocol on the cycle ergometer. The exercise protocol will be as follows: after 3-min of baseline measurements and 3-min of unloaded pedalling, the work rate will be increased by 10-25 Watt every 1-min to the limit of tolerance. During each test, arterial oxygen saturation (SpO2%) will be obtained by a pulse oximeter connected to the metabolic cart. Blood pressure will be monitored automatically via

a cuff that is connected to the metabolic cart at predetermined time points. The modified Borg 1-10 scale will be used to rate the magnitude of perceived dyspnoea and leg discomfort every 3-min throughout the test and at the end of exercise.

#### *Functional capacity*

The 6-min walk test (6MWT) will be performed according to the instructions of the American Thoracic Society, i.e.: the maximum distance walked by each patient on a 20-meter hospital corridor in 6 minutes will be assessed. Intensity of dyspnoea and leg discomfort will be assessed by the modified Borg 1-10 scale, whereas heart rate (HR) and SpO2% will be recorded at rest and at the end of 6MWT. Moreover, Short Physical Performance Buttery Test (SPPB) will be performed prior and following the completion of the 3-month period.

#### *Daily physical activity*

Daily physical activity was assessed for a period of seven consecutive days, one week prior and one week following the completion of the PR program, using a free application installed in the patients' smartphones (Leap Fitness Group). Patients instructed to have their phone in their pocket for as much as possible during the seven day period in order to minimise the data loss.

#### *Exercise training protocol*

During the outpatient PR programme, patients will perform supervised exercise training consisting of 30 minutes interval aerobic exercise on electromagnetically braked cycle ergometers at 100% of peak work rate and resistance exercises for the upper body. During each training session dyspnoea and leg discomfort will be recorded on the modified 1-10 Borg scale, whereas HR and SpO2% will be continuously monitored by a portable pulse oximeter. Based on symptoms of breathlessness and fatigue reported at the end of each exercise session (i.e. both dyspnoea and leg discomfort <4 at the Borg scale), the exercise intensity will be increased by 5-10% of the baseline WRpeak in the next session. The remote 24 home-based PR sessions will be consisted of 30 minutes walking with an individualised target of steps (recorded via the mobile app installed in the patients' mobile phone). The steps, leg discomfort and dyspnoea symptoms will be reported by the patient using a physical activity diary on a weekly basis. The assessors will set new step targets based on the steps and the symptoms reported by the patient. If dyspnoea and leg discomfort are both <4 at the Borg scale the weekly target of steps will be increased by 5-10%, otherwise the target will remain the same.

### *Statistical analysis*

Normal distribution of the data will be checked with the Shapiro-Wilk test. Comparisons of baseline characteristics will be made using independent t-test. Two-way ANOVA with repeated measures will be applied to detect differences between the two sexes across different time points. The LSD post hoc correction method will be used where appropriate. A p value <0.05 is considered significant.

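### Cheap improvement: the planned sex-by-time test pools the variance of men and women, so its 5% level is not assured if the sexes differ both in number and in SD of change

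*Combined protocol and SAP*

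**What the plan says.** The Study design section sets the question: "This study is a retrospective, single centre study, comparing the rate of improvement in men and women with long COVID-19 syndrome". It gives two measurement occasions: "Assessment will be performed at baseline and following completion of the PR programme". The Statistical analysis section then specifies the model: "Two-way ANOVA with repeated measures will be applied to detect differences between the two sexes across different time points". I read this as the sex-by-time test, since the rate of improvement is what is being compared.

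The rest of that section gives one assumption check, "Normal distribution of the data will be checked with the Shapiro-Wilk test"; a baseline comparison, "Comparisons of baseline characteristics will be made using independent t-test"; a follow-up method, "The LSD post hoc correction method will be used where appropriate"; and a threshold, "A p value <0.05 is considered significant".

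The section names no check of equal variances, no unequal-variance test, no robust standard error and no model with a separate variance for each sex. The documents give no total sample size, number per sex, matching or SD. No confidence intervals are planned.

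**The concern.** A classical repeated-measures ANOVA uses one error term for both sexes. With two visits, this means the SD of within-patient change is assumed to be the same in men and women. If that fails and the groups also differ in size, the error term gives the wrong weight to each group's variance. The p-value is then too small when the smaller group is more variable, and too large when the larger group is.

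The groups are whoever completed the programme in the study window, so nothing makes them equal in number. Unequal spread of change is plausible for outcomes in absolute units, such as "quadriceps isometric muscle strength with a strain gauge Myometer and handgrip strength", work rate, walking distance and steps. The Exercise training protocol section raises intensity by 5-10% of the patient's own baseline peak work rate, and the weekly step target also by 5-10%. Absolute gains could therefore scale with baseline level. That is inference; the documents contain no SD that shows it.

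At stake is the calibration of the one comparison that the study is designed to make.

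**Working it through.** **No stated figure to reproduce.** The plan gives no sample size, power, effect size or SD.

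**Inputs from the documents.** Two visits (Study design); two-way repeated-measures ANOVA and a 0.05 threshold (Statistical analysis). Sidedness is not stated; the F test is non-directional, so I treat it as two-sided.

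**Inputs assumed.** Normally distributed changes, the group sizes, and the SD ratio R (more variable group divided by less variable group). None of these is in the documents.

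**Step 1: equivalence.** With two visits, the sex-by-time F equals the square of the pooled-variance t on post-minus-baseline change. A numerical check on simulated data gave 1.04372 for both.

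**Step 2: when pooling fails.** For group sizes n1, n2 and change SDs s1, s2:

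- pooled variance of the difference, V_pool = [((n1−1)s1² + (n2−1)s2²)/(n1+n2−2)] × (1/n1 + 1/n2)
- true variance, V_true = s1²/n1 + s2²/n2

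Let k be the larger n over the smaller n, and r the larger group's SD over the smaller group's SD. In large samples, in units of the smaller group's variance divided by its n, the gap V_pool − V_true is (r² + 1/k) − (r²/k + 1) = (r² − 1)(1 − 1/k). It is zero if r = 1 or if k = 1. Either equality is enough.

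**Step 3: size under assumed inputs.** The approximate true level is 2[1 − Φ(1.96 × √(V_pool/V_true))]. The less variable group has SD 1. Example, 40 v 20 with the smaller group more variable and R = 2: V_pool = [(39×1 + 19×4)/58] × (1/40 + 1/20) = 0.1487; V_true = 1/40 + 4/20 = 0.2250; √(0.1487/0.2250) = 0.813; level 11.1%.

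| Split | More variable group | R | V_pool | V_true | SE ratio | Level, formula | Level, simulated |
|---|---|---|---|---|---|---|---|
| 40 v 20 | smaller | 1.25 | 0.0888 | 0.1031 | 0.928 | 6.9% | 6.6-6.9% |
| 40 v 20 | smaller | 1.5 | 0.1057 | 0.1375 | 0.877 | 8.6% | 8.4-8.6% |
| 40 v 20 | smaller | 2.0 | 0.1487 | 0.2250 | 0.813 | 11.1% | 11.1-11.2% |
| 40 v 20 | larger | 1.25 | 0.1034 | 0.0891 | 1.077 | 3.5% | 3.4-3.6% |
| 40 v 20 | larger | 1.5 | 0.1380 | 0.1063 | 1.140 | 2.5% | 2.6-2.7% |
| 40 v 20 | larger | 2.0 | 0.2263 | 0.1500 | 1.228 | 1.6% | 1.7-1.8% |
| 33 v 27 | smaller | 1.25 | 0.0843 | 0.0882 | 0.978 | 5.5% | see below |
| 33 v 27 | larger | 1.25 | 0.0882 | 0.0844 | 1.023 | 4.5% | see below |
| 24 v 16 | smaller | 1.1 | 0.1128 | 0.1173 | 0.981 | 5.5% | see below |
| 24 v 16 | larger | 1.1 | 0.1174 | 0.1129 | 1.020 | 4.6% | see below |

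Simulation of the four mild settings gave 4.4% to 5.6%. At 20 v 20 the simulated level was 5.0-5.3% for every SD ratio tried up to 2. With equal SDs it was 4.9-5.1% at every split. A larger study does not remove the effect: at R = 2 with the smaller group more variable, 30 v 10 gave 15.6% and 60 v 20 gave 15.3%.

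**Step 4: the alternative.** The Welch test on change stayed at 4.8-5.1% in the 40 v 20 settings and at 4.9-5.3% over all splits from 20 v 20 to 32 v 8.

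**Step 5: its cost when variances are equal.** For a difference of 0.7 SD, power falls from 70.7% to 70.0% at 40 v 20 and from 57.9% to 56.8% at 30 v 15. At more extreme splits, with the difference set so that the pooled test has about 68.5% power, it falls from 68.5% to 64.9% at 30 v 10 (3.6 points) and from 68.6% to 62.6% at 32 v 8 (6.0 points).

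**The case against.** The strongest reply is that neither triggering condition appears in the documents. Every group size and SD ratio above is assumed, mild departures barely move the level, and the same remark could be made of any two-group ANOVA in an unmatched cohort. All of that stands. It rules out saying that this trial's test is miscalibrated. It does not remove the case for choosing a test that holds its level either way, since the plan secures neither equality.

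Several stronger readings are tempting, and the documents do not support them:

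- **False positives are inflated.** The direction depends on which sex is both smaller in number and more variable in change. Neither is stated, and the test could equally be conservative.
- **Men and women differ in strength or work rate, so the test fails.** What matters is the spread of change, not of raw values. Many outcomes are also bounded scores or questionnaires, for which nothing suggests a sex-specific spread.
- **Only equal group sizes protect the test.** Equal SDs of change protect it as well.
- **The planned confidence intervals are wrong.** None are planned; the point would apply only to intervals later derived from this ANOVA.

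It is also fair to object that Welch is not free. Its cost is small up to 2:1 and noticeable at 3:1 or 4:1 in small samples.

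**Conclusion.** The point holds as a cheap improvement. The planned sex-by-time test is exactly a pooled-variance test on change, and its 5% level depends on an equality, of numbers or of SDs, that the plan neither secures nor checks.

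The size is conditional on normal changes and the assumed inputs. At a 2:1 split with clearly unequal SDs, the true level could lie anywhere from about 1.7% to about 11%, depending on direction. Under mild imbalance the effect is too small to matter. Nothing in the documents shows which case applies, so the method cannot be called wrong as written.

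**What to change.** In the Statistical analysis section:

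1. State that the sex difference in post-minus-baseline change is tested and estimated, for each outcome, with a Welch (unequal-variance) t-test and its 95% CI, in place of the pooled interaction F. If covariates are added, use a linear model with HC3 standard errors or a model with sex-specific variance.
2. Use the unequal-variance form for the baseline t-tests and for any between-sex post hoc comparison. Changing the interaction test alone would leave these on a pooled error term, as LSD in its standard form uses.
3. Report n and the SD of change for men and women for each outcome, so that readers can see whether the choice mattered.

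This takes a few sentences and no new data. The price, if variances are in fact equal, is the loss of power shown in Step 5.
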